Monitoring physical health and safety. All assessment visits will be conducted at a central location and all testing sessions will be conducted and supervised by a trained and certified research staff that will monitor potential adverse experiences and symptoms. At each visit, participants will be asked to report any adverse events they have experienced since their last visit. Immediate medical treatment will be provided for any illness or injury resulting from this study. Trained nursing staff members are present in the research center at all times, and a physician will also be available to evaluate the participant if needed.

In addition to the assessments conducted at in-person study visits, participants will be contacted by phone on a weekly basis between the end of training and the 12-week follow-up visit and will be asked to report any adverse events that have occurred since their previous phone contact or study visit. Specifically, they will be asked about any adverse events, including itching, pain, nausea, headache, etc. they have had.

Participants will also be asked about their mood, including depressive symptomatology, and other health related activities (i.e., physical activity), as well as general health status. Based on reported symptoms, participants may be asked to come in for an additional follow-up assessment visit with one of the healthcare professionals on the study team (i.e., physician or psychologist) for further evaluation of their symptoms. Based on information obtained at this visit, participants will then be referred for follow-up assessment and/or treatment with the appropriate healthcare provider.

Monitoring mental health and safety. At each assessment visit, participants will complete the BDI to assess for depressive symptom severity. Any participant who endorses clinical levels of any psychiatric disorder or who endorses suicidality will be referred to [name], study psychologist, for further follow-up assessment. The psychologist will then provide a recommendation regarding the appropriate course of follow-up and also advise on whether it is safe for the participant to continue in the study. If a participant is found to be actively suicidal with a plan and/or intent, they will be escorted immediately to the emergency room at the Shands Hospital at the University of Florida. If safety is an issue, UF security or local authorities will be called for assistance. If a participant endorses suicidal thoughts or significant psychopathology, participants will be referred for further evaluation with [name] (Licensed psychologist and co-investigator). Based on this evaluation, she will recommend follow-up assessment and treatment appropriate to the situation including treatment at the Psychology and/or Psychiatry Clinics within Shands Hospital at the University of Florida.

Adverse Event Reporting. An **adverse event (AE)** is defined as any unfavorable and unintended sign (including an abnormal laboratory finding), symptom, or disease temporally associated with the intervention irrespective of whether it is considered related to the intervention.

Non serious adverse events. Defined as conditions that may be unpleasant and bothersome to the participant that does not require discontinuing the study.

Serious adverse events (SAEs). Defined as events that may be harmful to the participant and/or may be serious enough to warrant either temporary or permanent discontinuation of the study intervention, either because they are intolerable or because they are judged to be potentially harmful. All serious adverse events require immediate reporting and an assessment of the implications for the continuation of the study and/or modification of the consent form. The following are considered serious events:

- It is acute or life threatening;
- It results in prolonged, permanent or severe disability;
- It is another severe illness including worsening of a pre-existing condition, injury or accidents;
- It is an inpatient hospitalization or surgical procedure, or a treatment to prevent a serious event;
- It results in death;
- It is a clinically significant abnormal laboratory or diagnostic test.

Table 3. Adverse Event (AE) Classification

Adverse Event (AE) Classification	
Definite.	Temporal pattern + known or expected AE response pattern + confirmed by stopping the intervention + reappearance of AE on re-challenge
Probable.	Temporal pattern + known or expected AE response pattern + confirmed by stopping the intervention + could not be explained by participant's clinical state
Possible.	Temporal pattern + known or expected AE response pattern + could have been produced by a number of other factors
Unknown.	Relationship for which no evaluation can be made
Not related.	AE for which sufficient information exists to indicate that the cause is unrelated to the study intervention

Classification of AE severity. The principal investigator will

evaluate adverse events for seriousness, expectedness, severity, and relationship to study intervention at each study visit. The primary mechanism for ensuring participant safety will be clinical observation of symptoms. The study will be conducted and supervised by trained study staff that are certified in CPR and will monitor potential adverse experiences and symptoms. During each visit, participants will log any health-related problems or symptoms they are experiencing. These sheets will be reviewed by study staff before allowing the participant to continue. Community health services will be contacted immediately if warranted by the participants' symptoms.

All adverse events (AEs) will also be categorized according to the likelihood that they are related to the study intervention. Specifically, they will be labeled either definitely, probably, possibly or unrelated to the study intervention. The classification of potential relationship to the intervention is shown in Table 3.

Effective screening will exclude individuals who would be at increased medical risk as a result of participation in this research. FMRI contraindications, such as claustrophobia or some metal implants will be assessed by telephone screening and again on the day of the scan. [name], who has completed MRI safety training and Protocol IRB #201400328

has over 4 years experience screening FMRI participants, will supervise these procedures. The RA who will conduct neuroimaging analyses will be trained in UF AMRIS safety procedures and will also be responsible insuring for participant safety. Adverse events, although unlikely, may occur as a result of neuroimaging.. Such events will immediately be reported by [name] (PI) to the local IRB, with serious adverse events reported to both the IRB and NIH.

SAE reporting. Serious adverse events (SAEs) that are unanticipated, serious, and possibly related to the study intervention will be reported within 24 hours of study's knowledge of the SAE to the Independent Monitor, IRB, and CTSA in accordance with the regulatory requirements. Anticipated SAEs or those unrelated to the study intervention will be reported to the same individuals/entities in accordance with regulatory requirements.

Minor events will be reported to the IRB at the time of annual review, as well as to the oversight committee on a bi-annual basis. Both the principal investigator and the study staff will review the study weekly and examine reports of adverse incidents and reports of study participant recruitment and follow-up. Throughout the course of the study, information regarding issues deemed critical to the study or to the safety of research participants will be provided to the principal investigator and other study investigators as needed. As a result of receiving this critical information, a meeting to discuss this information may be convened. Information deemed critical would include:

- serious and non-serious adverse events that may occur;
- suspicion of scientific fraud or misconduct;
- any other issues which may warrant protocol changes or modifications.

Adverse event (AE) and serious adverse event (SAE) determination and monitoring will be achieved via administration of structured questionnaires. Standardized forms for referring and treating study participants who experience adverse events will be in place.

Documentation of Training on Protection of Human Participants. All key personnel on the study have successfully completed and obtained certification from their respective institutions for Mandatory Education in Human Research Subjects Protection. The Mandatory Education is described as follows:

On August 23, 2000, an institutional policy was enacted requiring all clinical investigators and their key personnel to undergo mandatory education in human research subject protection. The program was initiated on September 1, 2000 and includes all clinical researchers regardless of source of research funding. At the core of the self-directed training program is the tutorial manual entitled, "Protecting Study Volunteers in Research" by Dunn and Chadwick. Each researcher receives a copy of the manual and, in a timely fashion, completes the test included in the manual. Each researcher must obtain a score of >86 to complete the certification requirements to conduct clinical research at this institution. In all cases, no researcher will be allowed to conduct clinical research without proof of human research subject protection education after September 30, 2001.

Additional and continuing education opportunities for clinical researchers include the Office of Research Administration newsletter that is circulated to approximately 900 recipients every 6 weeks. Relevant information concerning research review is available on the UF ORA web page. In addition to standard institutional research information, the web page contains links to other sites such as CenterWatch, NIH.

8. Possible Benefits:

There are well-documented benefits for older adults who participate in cognitive training, including improvement in working memory, attention, and executive functions. Deficits in these cognitive abilities significantly impact quality of life, financial capacity, medication adherence, and mortality in older adults. All participants undergoing CT may benefit from these effects. Those participants randomly assigned to the active tDCS+CT treatment group may experience further benefit beyond that of cognitive training alone. Benefits to society will include the contribution of novel data regarding the efficacy of neuromodulation methods for enhancing cognitive training effects in older adults. This may help inform treatment protocols in a growing segment of the US population (i.e., those 65 years and older). Data collected from this study will serve as a foundation for larger clinical studies that examine optimized methods for treating aging-related cognitive decline using cognitive training and tDCS. Some participants may not benefit from the study at all.

9. Conflict of Interest:

None

References:

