Aim 1. Determine whether neurocognitive improvement and longer-term functional outcome (as measured by “ecological assessment”) are better when CT is coupled with tDCS, an intervention that will increase neural plasticity and augment training effects.

H1.1. Active tDCS combined with CT will amplify effects of CT on measures of attention, working memory, executive functioning, and learning efficiency, while sham tDCS will not.

H1.2. Active tDCS will enhance near and far transfer of CT, but sham will not evidence near or far transfer.

Aim 2. Determine whether CT combined with tDCS leads to greater functional and metabolic brain changes (fMRI, MRS). Effects will parallel Aim 1.

H2.1. Combined CT + tDCS will potentiate decrease activation in working memory and attentional (dorsolateral prefrontal cortex, medial frontal cortex, inferior parietal lobe, supplementary motor association cortex) brain systems, reflecting increased neural efficiency, while CT + sham tDCS will not.

H2.2 Cerebral metabolite alterations will occur secondary to CT and tDCS, with long-term increase in GABA and *N*-acetyl aspartate (NAA) concentrations, and decreased choline (Cho) and myoinositol (MI) concentrations in the frontal cortex and posterior parietal cortex. CT and tDCS will modulate MRS GABA in frontal areas. These effects will be specific to CT.

Secondary aim. We will examine which baseline factors (e.g., clinical, demographic, neuroimaging, cognitive) best predict individual differences in outcome.

6. Research Plan:

6.1. Experimental design. This study employs a randomized trial design with 90 participants. One factor with two levels [Factor 1 = stimulation type (active or sham)] yields two cells. Thus, participants will be assigned to one of two conditions:

1: Active tDCS + CT

2: Sham tDCS + CT

CT has previously been established with strong effects on cognitive and functional outcomes. Some small clinical trials showed small to medium effects of tDCS in conjunction with CT.

Participants will be assessed at three primary time points during the study, plus one screening visit on the front end to be sure they meet all inclusion criteria for the study:

- 1) Informed Consent and Screening Visit
- 2) Assessment Visit #1- baseline pre-training;
- 3) Assessment Visit #2- post-2 weeks
- 4) Assessment Visit #3- three month follow-up after all training
(see Figure below for summary).

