This design will enable longitudinal analyses of CT and tDCS effects. We will examine their effects on cognitive performance, functional and metabolic neuroimaging measures, and everyday functional abilities. At each assessment, we will obtain clinical and medical history, neurocognitive measures, and neuroimaging (structural MRI,

FMRI, MRS). All participants will undergo neuroimaging at baseline, following training, and at a three month follow-up.

Stimulated Brain Study

Screening	✓	✓	✓	✓			✓		
Assessment Visits 1-3 Activity Summary	Informed Consent Form	Medical History	Hearing and Vision Tests	Memory and Thinking Tasks	Computerized Daily Activity Tasks, like banking etc.	Physical and Medical Self Reports	MRI Screen-Form	NIH tool box	MRI Brain Scan Appt.
Visit #1 Baseline				✓	✓	✓	✓	✓	✓
Visit #2 After 2 weeks (10 days) of Training				✓	✓	✓	✓	✓	✓
Visit #3 Three month followup				✓	✓	✓	✓	✓	✓
Daily Lab Visits	Brain Training Games	Brain Stimulation/Sham	tDCS Sensation Questions						
Days 1-10	✓	✓	✓						

6.2. Study participants and randomization procedure. We will recruit 90 older adults (women = 45; age: 65-90 years). Study participants will consist of healthy individuals who have expressed an interest in taking part in an intervention aimed at optimizing and possibly preserving cognitive functioning and brain health. We will use web-based permuted block randomization to randomly divide participants into the four groups. People with pre-existing dementia, neurological brain disease, or meet criteria for a diagnosis of mild cognitive impairment (MCI) will be excluded, though people with subjective concerns about their cognitive functioning, who do not meet these criteria, may participate. Detailed inclusion/exclusion criteria can be found in Section 7.

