6.2.1. Experimental Design Considerations and Limitations: CT Approach. The POSITScience BrainHQ treatment program was selected because it 1) provides specific training tasks directed at three essential cognitive domains tied to our aims and hypotheses (attention, working memory, executive control) that correspond with the neurocognitive and functional neuroimaging measures to be studied; (2) is shown to produce significant cognitive and functional improvements with good effect sizes in past RCTs (ACTIVE) with up to 10 year durability and transfer of training to measures of self-reported everyday functioning; 3) provides a “cognitive treatment engine²⁸²” which alone has a very highly likelihood of yielding significant cognitive and functional improvements, enabling us to test the augmenting effects of tDCS; and 4) is computerized, well standardized, and efficiently implemented.

Combined CT. We selected a combined CT approach rather than testing one specific training task: 1) This would optimize CT treatment effects for this primary intervention, providing a strong and reliable engine of change with which to examine effects of tDCS; 2) This approach enables us to affect several related cognitive functions that are strongly dependent on neural plasticity of the frontal cortex; and 3) This approach would maximize participants interest and motivation versus a single task that could become boring.

tDCS. Brain stimulation provides a means of directly augmenting CT effects. tDCS was selected from possible alternatives (e.g., transcranial magnetic stimulation) based on research and data by [name] (PI), [name], and [name] (consultants), including its safety profile, ability to facilitate neural plasticity, and potential for application outside of research settings. Frontal stimulation was chosen based on prior and preliminary studies demonstrating significant impact on attention, working-memory, and other cognitive abilities to be trained during CT. 2mA tDCS was chosen based on prior research demonstrating that this parameter excites, rather than inhibits, activity in stimulated neurons.²⁸³

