tasks. Training platform. CT employs a PositScience BrainHQ suite via its researcher portal. These tasks are web-based and multi-platform (i.e., Windows, Mac). Participants will be randomly assigned to training on 4 tasks focusing on working memory or 4 tasks focusing on attention/speed of processing. Participants will be required to have a specific viewing distances. Study interventionists will provide daily performance summaries. The rationale and task demands for each component were described earlier (A.3.3). These CT are commercially available (www.positscience.com), with well-documented protocols/manuals (See Appendix 1) and thus not described in detail here. (See miscellaneous attachments for specific game descriptions.)

Hardware

Participants will complete CT on computers located at Clinical Translational Research Building. Support: Participants will have the opportunity to ask questions, and will be instructed on the various computer tasks. No special technical skills or experience are required. A support phone number will be available if participants have questions arise between study visits.

6.5. Transcranial Direct Current Stimulation:

Bilateral Frontal tDCS: A Soterix Clinical Trials Direct Current Stimulator will apply 20 minutes of 2.0mA direct current through two biocarbon rubber electrodes encased in saline soaked 5cm² sponges (8cc of 0.9% saline solution) which then may be covered with electrode paste, and placed over the frontal cortices at F3 and F4 (10-20 system). Based on our well-established computational modeling workflow (C.4.1), F3/F4 stimulation delivers a broad pattern of frontal stimulation (see C.4.1d). Current inflow will occur on the right (F4), and outflow on the left (F3). Impedance quality will be $\leq 10\text{k}\Omega$ to insure proper stimulation of brain tissue.

Sham tDCS: Sham stimulation is performed with the same device and all procedures will be identical except for the duration of stimulation. Participants will receive 30 seconds of 2 mA of direct current stimulation at the beginning of the session.

Participants habituate to the sensation of tDCS within 30-60 seconds of stimulation. This procedure provides the same sensation of tDCS without the full duration of stimulation, making it a highly effective sham procedure. Blinding: The device has built in RCT double blinding protocols. Soterix will communicate only with [name] (Co-Mentor/statistician) to de-identify data for analyses.

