6.6.1. fMRI paradigms. We will present the two fMRI tasks (2-Back, Spatial-Temporal Attention) using E-Prime 2 software (Psychology Software Tools, Inc., Pittsburgh, PA), with the video signal on a screen behind the participant's head. The screen is viewed through a double-mirror attached to the head coil. An MR-compatible piano-key response box attached to the stimulus presentation computer will collect performance data. We will apply a cushioned-pillow head stabilizer to minimize head movement during scanning.

[figure not shown]
2-Back. *This task will measure brain changes due to our N-back training.* We will assess verbal working memory on a 2-Back task, as in past studies^{153,157}. Consonants are visually presented for 500ms with an ISI=2500ms. Participants determine if each stimulus is the same or different from previously stimuli, responding by binary button press (yes vs. no). Executive control, phonemic buffering, and sub-vocal phonemic rehearsal are required. 0-back and 2-Back conditions are alternated in a block design with two 5-minute runs of eight blocks (consonant lists), with four blocks of the 0-Back and four blocks of the 2-Back. *0-Back:* Four blocks of nine consonants of random case and order (33% targets). Yes-no responses are made if targets that match stimuli occurring two earlier. *2-Back:* Four blocks of 15 consonants (33% targets) will be pseudorandomly presented across the visual field. Accuracy and RT are recorded.

The useful field of view (UFOV) fMRI task. Task will involve participants making decisions about where on the screen they saw a previously displayed object.

[figure not shown]
Participants are presented two images simultaneously, one in a central box, and another outside the box. These images disappear very quickly and are replaced by a "noise" screen, similar to a scrambled television signal. Then participants are asked where they saw the object (a car) outside the box (e.g., up, down, left, right, etc.) and

what object was inside the box (either a car or a truck). The participants will respond using buttons on a response box. After participants have answered they are presented a fixation cross and wait until the next trial begins. Time between trials is randomized and jittered in accordance with best practice event-related fMRI design. The task duration is approximately 17 minutes. Examples of the stimuli are below.

1) Both objects are presented simultaneously

2) Noise Screen

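### If each participant trains only one task set, a two-cell active–sham comparison on a single domain mixes trained with untrained people, and the plan does not say how task set enters the analysis

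*Combined protocol and SAP*

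**What the plan says.** The protocol describes the training and the design in ways that do not fit together.

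- Section 6.4 (Cognitive Training): "Participants will be randomly assigned to training on 4 tasks focusing on working memory or 4 tasks focusing on attention/speed of processing". Section 4.3.3 lists the same two sets of four. The N-back-type tasks (Card Shark, Auditory Aces) appear only in the working-memory set, and Double Decision only in the attention/speed set.
- Section 6.1 (Experimental design): "One factor with two levels [Factor 1 = stimulation type (active or sham)] yields two cells". Task set is not a factor.
- Section 6.2 (Study participants and randomization procedure) promises "web-based permuted block randomization to randomly divide participants into the four groups", without naming the groups.
- Section 6.2.1, Combined CT: "We selected a combined CT approach rather than testing one specific training task", with the reason that "This approach enables us to affect several related cognitive functions".
- Section 5, H1.1: "Active tDCS combined with CT will amplify effects of CT on measures of attention, working memory, executive functioning, and learning efficiency". There is no restriction by the set trained. H1.2 separately predicts near and far transfer, and H2.1 predicts changes in both working-memory and attentional systems.
- Section 6.6.1, 2-Back: "This task will measure brain changes due to our N-back training". The UFOV task has no comparable sentence; Section 6.2.1 only relates the active fMRI tasks in general terms to the functions being trained.

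No allocation ratio is stated for stimulation or for task set. No significance level, power, SD or analysis model is given either.

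**The concern.** Under Section 6.4 a working-memory test is a trained-domain outcome for some participants and a transfer outcome for the rest; an attention test is the reverse. Section 6.1 offers the only stated structure, two cells, and that structure averages over a factor the trial itself randomises. A single-domain active–sham difference read that way has two problems. It combines people in whom tDCS had training in that domain to amplify with people in whom it did not. It also merges what H1.1 asks (amplification of training) with what H1.2 asks (transfer), so neither a positive nor a null result could be assigned to one hypothesis. In a trial of 90 people with small-to-medium expected effects, the loss of signal could decide the result.

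**Working it through.** **Inputs from the documents.** Total enrolment is 90 (Section 6.1). Section 6.1 describes prior tDCS-plus-CT effects only in words, as small to medium. Section 4.3.3 puts CT effects above d = 1.0 immediately after training.

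**Assumptions, because the documents give no figure.** 45 per arm; two-sided 5%; SD of 1; trained-domain effect d = 0.5, with 0.35 and 0.2 as lower cases; equal task-set split, p = 0.5, unless varied.

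**Plan's own figure.** The enrolment of 90 cannot be reproduced, since no power calculation accompanies it. By the normal approximation, 45 per arm detects (1.960 + 0.842) × √(2/45) = 0.59 SD with 80% power.

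**Step 1: dilution.** If people trained in the tested domain have effect d and the others have effect k × d, the two-cell contrast estimates

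d × [p + (1 − p)k].

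With p = 0.5 the multiplier is (1 + k)/2.

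**Step 2: power (two-sample t-test, 45 per arm, p = 0.5).**

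| k | multiplier | d = 0.5: effect, power | d = 0.35: effect, power | d = 0.2: effect, power |
|---|---|---|---|---|
| 0 | 0.50 | 0.25, 22% | 0.175, 13% | 0.10, 8% |
| 0.5 | 0.75 | 0.375, 42% | 0.2625, 23% | 0.15, 11% |
| 1 | 1.00 | 0.50, 65% | 0.35, 37–38% | 0.20, 16% |

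**Step 3: the split matters.** With k = 0 and d = 0.5, p = 1/3 gives 0.5 × 1/3 = 0.167 and power of about 12%. With p = 2/3 the effect is 0.333 and power about 35%. One half is therefore not a ceiling on the loss.

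**Step 4: leaving task set out also adds variance.** Suppose CT itself moves the trained domain by 1.0 and the other domain by nothing. With an equal split the sham variance is 1 + 0.25 × 1.0² = 1.25 and the active variance is 1 + 0.25 × 1.5² = 1.5625. The average is 1.406, so the SD is 1.19. The k = 0 effect becomes 0.25/1.19 = 0.21 SD, with power of about 17%.

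**Step 5: alternatives at d = 0.5.**
- Restrict each domain's test to those trained in it: 90/4 = 22.5 per arm, power about 37–38%.
- Score every participant on their own trained-domain composite: all 90 contribute and power is 65%, provided the standardised effect is the same in both sets.
- Test the stimulation × task-set interaction on one domain: SE = √(4/22.5) = 0.42 SD, so this term can be estimated but only roughly.

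**The case against.** The strongest reply is that no analysis is specified, so nothing has yet been pooled. That stands. A reader might infer that every test in the plan mixes trained and untrained people, but the documents support less: the only stated structure is two cells, the mention of four groups would fit stimulation × task set, and the handling of task set is open.

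The premise is also unsettled. Section 6.2.1 describes combined training, and if that is what is delivered the dilution disappears. The detailed wording of Section 6.4 and the two four-task lists point towards single-set training, but the sponsor has to say which is meant.

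Three further readings go too far.

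- *The effect is cut by up to half.* This needs an equal split and no carry-over. H1.2 expects transfer, all active participants receive the same frontal stimulation, and Section 6.2.1 calls the trained functions related, so k = 0 is an extreme case. An uneven split could cost more than half.
- *Both fMRI tasks are treated as if everyone had been trained on them.* Only the 2-Back is credited to a specific training. Even there, attention trainees could serve as a randomised comparison group for N-back training, provided task set is in the model. Section 6.1 does not put it there.
- *Executive functioning belongs to neither set.* Section 6.6.1 names executive control among the demands of the 2-Back, and N-back-type tasks sit in the working-memory set. The trained/untrained division does not settle where those measures belong.

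An effect averaged over task sets is a legitimate estimand if chosen deliberately; the plan does not state that choice. Section 6.4 does schedule a 20-minute composite of the training tasks for everyone, but it does not tie it to a hypothesis or say how it is divided by task set. The study calls itself a pilot and exploratory, which lowers the stakes of low power but does not remove the ambiguity.

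**Conclusion.** The point holds in conditional form. The sections contradict each other on whether training is single-set or combined and on whether there are two groups or four, and no text says how a randomised task set enters the analysis. If Section 6.4 is right and the arms are compared as two cells, the single-domain contrast shrinks by p + (1 − p)k. At the assumed d = 0.5, equal allocation and two-sided 5%, power runs from 22% (no carry-over) through 42% (half carry-over) to 65% (no dilution). The split, the carry-over, d, the SD and the significance level are all assumptions. What does not depend on them is that H1.1 and H1.2 cannot be separated on a single-domain outcome unless task set is taken into account.

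**What to change.** 1. Reconcile Section 5 (H1.1), Sections 6.1 and 6.2, the Combined CT paragraph of 6.2.1, Section 6.4 and the 2-Back text of 6.6.1. State the allocation ratio for both assignments.
2. If single-set training is confirmed, describe the design as stimulation × task set, and include task set and the stimulation × task-set term in the models.
3. Before unblinding, fix which of the tests already collected form the working-memory composite and which the attention/speed composite, each standardised.
4. Test the trained-domain part of H1.1 on each participant's own trained-domain composite, adjusted for task set, so that all 90 contribute. Report the untrained-domain composite as transfer under H1.2. Leave it to the investigators to decide, and record, where the executive and learning measures belong.
5. For H2.1, analyse 2-Back and UFOV activation separately, each with task set and its interaction with stimulation. Do not pool them: one is a block design and the other event-related, and nothing shows that their contrasts share a scale.

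The cost is analysis and protocol wording; no new data are needed. The limits are that the test-to-domain mapping must be prespecified, the composite test assumes similar standardised effects in both sets, and estimates within one set (about 22 per arm if allocation is equal) will be imprecise.
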